## 1. Study Identification. HospitalCG 034/18 clinical study

**Brief Title:** Supplementation of Thyroid Hormone for TSH Control in Patients With Chronic Kidney Disease Without TRR. (TSHrenal) .

**Acronym:** TSH-renal

**Official Title:** Supplementation of thyroid hormone for TSH targets in patients with chronic kidney disease without renal substitution therapy: randomized, double-blind clinical trial at the Guadalajara Civil Hospital.

**Study Type:** Interventional (clinical trial).

## 2. Study Status

- Record Verification Date: march 15, 2019
- **Overall Recruitment Status:** Completed: The study has concluded normally; participants are no longer receiving an intervention or being examined (that is, last participant's last visit has occurred)
- **Study Start Date:** October 1, 2018
- **Primary Completion Date:** January 31, 2019
- **Study Completion Date** March 1, 2019.

## 4. Oversight

U.S. FDA-regulated Drug: no

U.S. FDA-regulated Device: no

U.S. FDA IND/IDE: no

Human Subjects Review: Board Status: Approved Approval Number: 034/18

Board Name: Ethics Committee 034/18

Board Affiliation: Hospital Civil de Guadalajara

[contact] Ext: 2584

Email: [[contact]](mailto:[contact])

Address: [name]

Data Monitoring: no

FDA Regulated Intervention: no

## 5. Brief Summary:

Study design: Phase II study, randomized, double-blind, unicentric, two-arm, placebo-controlled clinical trial. Methods and participants: Patients with Chronic Kidney Disease G2-G5 with proteinuria without renal replacement therapy, who come to the clinic of renal

health clinic of the Fray Antonio Alcalde civil hospital. As criteria for non-inclusion, need for dialysis, primary hypothyroidism or pre-existing thyroid disease, ischemic heart disease in a period less than 6 months, arrhythmia, pregnancy, use of drugs that interact with synthesis of thyroid hormones, do not accept informed consent, thyroid stimulating hormone (TSH)  $<2.5 \text{ uiml / L}$  or  $\text{TSH} > 10 \text{ uiml / L}$ .

## **6. Detailed Description:**

Thyroid disorders, especially elevated TSH levels in patients with CKD, are frequent. As it is an easy medication to acquire and of little cost compared to the other options, levothyroxine would provide benefits already known in patients with CKD and also a proteinuria effect (knowing each other). as a factor of progression of the CKD a health problem worldwide) being a potentially useful treatment and a dose that the risk is minimal. The study consists of 3 phases, the first phase consists of capturing patients from the renal health clinic, having baseline measurement of the variables. Then, the second phase consists of both groups treating them with medication (levothyroxine with a safe dose for the investigator's population with high cardiovascular risk of 0.25mcg so that the patient's weight range between 50-80kg maintains a dosage of 0.3-0.5mcg / kg / day that the thyroid axis is not affected) of fasting levothyroxine (in the case of taking a drug that interacts with absorption changes its use according to the specified hours, see Table 2) or placebo according to the randomization 1: 1 for three months and that have treatment with ACEI or ARA-2 (specifying which and the dose thereof), with follow-up every 4 weeks (Monitoring thyroid function). The third phase consists of a comparison of the variables studied.

The primary objective is to evaluate the effect of the use of levothyroxine on the levels of proteinuria measured on the test strip of the general urine and protein examination in 24-hour urine patients with chronic kidney disease without renal support therapy with proteinuria, who already receive the standard antiproteinuric treatment with an ACE inhibitor or ARA-2 against placebo and the secondary objectives are to evaluate the changes in proteinuria, according to TSH levels in 2.5-9.9  $\mu\text{iml / L}$ , with the levels of T4L in levels 0.8-1.8mcg / ml), analyze improvement in glomerular filtration rate in patients receiving levothyroxine and at the end of the study and evaluate Tolerability and safety of levothyroxine as antiproteinuric treatment in chronic kidney disease without renal support therapy, and as secondary objectives improvement in cholesterol, triglycerides blood pressure. Any adverse event will be recorded in the adverse event reporting forms. (definition of the International Conference on Harmonization [ICH])

- Study Type: Interventional

Actual Enrollment: 32 participants

Allocation: Randomized

[figure not shown]
Intervention Model: Parallel Assignment

Phase II study, type placebo controlled clinical trial, randomized of two arms, double blind, unicentric.

Masking: Triple (Participant, Care Provider, Investigator)

The study drug and placebo will be packaged and labeled on the basis of this randomization program, being letters both, for placebo or Levothyroxine, coding that only the third randomization investigator outside the study will know. The letters of the drugs will be preprinted on the study drug labels and will be assigned to double blind treatment as the subjects meet the requirements for the study. Both groups treated with fasting medication (levothyroxine) (in the case of taking a drug that interacts with absorption, use of the drug is changed according to the specified hours, see Table 2) or fasting placebo according to the randomization 1: 1 3 months

## **Participant Flow**

## Arms and Interventions

Arm	Intervention/treatment

Active Comparator: Group with levothyroxine
 
Patients with Chronic Kidney Disease G2-G5 with proteinuria without renal replacement therapy, who comes to the clinic of renal health clinic of Fray Antonio Alcalde civil hospital. That meet the inclusion criteria. Levothyroxine 25 mcg (1/4 tablet of 100mcg) was administered in fasting the first month, the doctor evaluated with monthly control of TSH levels (if the TSH level was not in the range of TSH 1-2.5 uim / L the second month increase to a dose of 50 mcg (1/2 tablet of 100mcg fasting, or similarly if the patient had a TSH <1 u / L was suspended in medication and it was valued restart the next month the medication if TSH> 2.5u / L ) to complete three months of intervention.
	
Drug: Levothyroxine
 
levothyroxine with a safe dose for our population with high cardiovascular risk of 0.25mcg so that the patient's weight range between 50-80kg maintains a dosage of 0.3-0.5mcg / kg / day that does not affect the thyroid axis) fasting levothyroxine (in the case of taking a drug that interacts with absorption, use of it is changed according to the specified hours, see Table 2), and adjusted according to TSH levels > 1 and normal T4L
 
Other Names:
 
 
• placebo
 


Placebo Comparator: Group Placebo
 
Patients with Chronic Kidney Disease G2-G5 with proteinuria without renal replacement therapy, who comes to the clinic of renal health clinic of Fray Antonio Alcalde civil hospital. that meet the inclusion criteria.
 
Placebo (1/4 tablet) was administered in fasting the first month, the doctor assessed with monthly control of TSH levels (if the TSH level was not in the range of TSH 1-2.5 UM / L the second month increase at a dose (1/2 tablet fasting, or similarly if the patient had TSH <1 u / L was suspended in medication and it was valued restart the next
	
Drug: Levothyroxine
 
levothyroxine with a safe dose for our population with high cardiovascular risk of 0.25mcg so that the patient's weight range between 50-80kg maintains a dosage of 0.3-0.5mcg / kg / day that does not affect the thyroid axis) fasting levothyroxine (in the case of taking a drug that interacts with absorption, use of it is changed according to the specified hours, see Table 2), and adjusted according to TSH levels > 1 and normal T4L
 
Other Names:
 
 
• placebo
 

month the medication if TSH> 2.5 / month) to complete three months of intervention.

## Eligibility Criteria

---

Ages Eligible for Study: 18 Years and older

Sexes Eligible for Study: All

Accepts Healthy Volunteers: No

## Criteria

### Inclusion Criteria:

- Patients older than 18 years
  - Patients with chronic kidney disease G2-G5 without renal replacement therapy) who attend a renal health clinic.
  - Presence of proteinuria in a test strip, 24 hours urine collection (greater than 150mg / dl in 24hrs urine)
  - TSH <9.9uiml / L and TSH> 2.4 0uiml / L
  - Take an IECA or ARA-2
  - Patients with weight> 50 kg and <80kg
  - Accept informed consent

### Exclusion Criteria:

- Chronic dialysis (peritoneal dialysis or hemodialysis)
  - Primary hypothyroidism or preexisting thyroid disease
  - Use of levothyroxine.
  - TSH> 10uiml / L and TSH <2.5 0uiml / L
  - Positive thyroid antibodies
  - Ischemic heart disease in less than 6 months
  - Cardiac arrhythmia
  - Use Medications (Levothyroxine synthesis, see Table 2)
  - Anxiety disorder
  - Pregnancy

- Do not accept consent
- Patients weighing <50 kg and > 80kg

### **Baseline Measure Information**

Table 1. Baseline characteristics of both groups

	Placebo (n= 14 patients)	Levothyroxine (n=18 patients)	P value
Sex (n=% female)	71.42%	55.55%	NA
Age (years)	63.85 DE+/- 15	69.22 DE+/- 8.7	0.41
Diabetes Mellitus (yes or no)	11 (78.57%)	13 (72.22%)	1.00
Hypertension (yes or no)	12 (85.71%)	16 (88.88%)	1.00
Weight (Kg)	67.90 +/- 13.83	67.01 +/- 11.32	0.88
Obesity (BMI >30 kg/m  )	1 (7.14%)	3 (6.6%)	0.61
ERC G3a (45-59 ml/min/1.73m  )	0	3 (6.6%)	0.23
ERC G3b (30-44 ml/min/1.73m  )	2 (14.28%)	4 (22.22%)	0.67
ERC G4 (15-29 ml/min/1.73m  )	5 (35.71%)	7 (38.88%)	1.00
ERC G5 ( <15 ml/min/1.73m  )	7 (50%)	4 (22.22%)	0.14
eGFR (ml/min/1.73m  )	9.96 +/- 18.3	13.35 +/- 28	0.16
TSH (uim/L)	4.46 +/- 1.68	5.93 +/- 2.2	0.02 ®
Protein urine 24/hours (gr/24hrs)	1.28 +/- 1.28	1.71 +/- 1.20	0.14
Cr.s (mg/dl)	3.65 +/- 1.65	2.46 +/- 1.13	0.05 ®
Albumine (mg/dl)	3.99 +/- 0.41	3.8 +/- 0.41	0.24
Tryglicerides (mg/dl)	194 +/- 75.3	144.66 +/- 91.76	0.09
Cholesterol (mg/dl)	170.57 +/- 45.96	165.5 +/- 59.67	0.67
LDL (mg/dl)	75.5 +/- 19	102.38 +/- 31.42	0.01 ®
Hemoglobin (gr/dl)	11.37 +/- 1.21	11.95 +/- 1.61	0.17
BP systolic (mmHg)	148.14 +/- 27.7	160 +/- 19.4	0.17

BP diastolic (mmHg)	79 +/- 11.72	81.83 +/- 8.2	0.60
IECA o ARA-2 (n=%)	100	100	1.00
Allopurinol (n=%)	100	100	1.00
Statines (n=%)	100	100	1.00

- Study-Specific Measure
- Age:
  - Age, Continuous:
  - Age, Categorical:
    - >18 and <80 year
  - Age, Customized: Customizable age categories
- Sex/Gender
  - Sex: Female, Male
- Race and Ethnicity
  - Race and Ethnicity Not Collected (Hispanic race)
- Region of Enrollment: Guadalajara, Mexico
  - **Measure Type:** Mean

**Measure of Dispersion** Standard Deviation

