### Secondary Outcome Measures:

1. Estimated glomerular filtration rate (eGFR) in patients with subclinical hypothyroidism and CKD G2-G5 without renal support therapy Randomized clinical trial of levothyroxine group versus placebo [Time Frame: three months]

Outcome Measure Description [\*] Definition: Outcome Measure Description [\*]

Definition: the glomerular filtration rate was calculated based on the seric creatinine expressed in mg / dl, the formula of CKD-EPI was use.

Measure of Dispersion/Precision: Standard Deviation

Number of Participants Analyzed: 32patients

Number of Units Analyzed: (18 arm Levothyroxine and 14 arm placebo)

Unit of Measure eGFR ml/min/1.73m^2

2. Measurement of lipid profile (cholesterol, LDL and triglycerides) in patients with subclinical hypothyroidism and CKD G2-G5 without renal support therapy Randomized clinical trial of levothyroxine group versus placebo. [Time Frame: three months]

Outcome Measure Description.

Definition: serum cholesterol, triglycerides and LDL cholesterol levels were measured in mg / dl at the beginning and at the end of three months for all patients

Measure of Dispersion/Precision: Standard Deviation

Number of Participants Analyzed: 32patients

Number of Units Analyzed: (18 arm Levothyroxine and 14 arm placebo)

Unit of Measure mg/dl

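### The baseline eGFR row of Table 1 contradicts the CKD stage counts printed in the same table: 13.35 +/- 28 is impossible for the levothyroxine arm

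*Combined protocol and SAP*

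**What the plan says.** All references are to the Combined protocol and SAP.

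- **Baseline Measure Information, "Table 1. Baseline characteristics of both groups".** The columns are placebo (n = 14) and "Levothyroxine (n=18 patients"). The stage rows run from "ERC G3a (45-59 ml/min/1.73m" down to "ERC G5 ( <15 ml/min/1.73m 2", each with its eGFR range in the label. The counts, placebo then levothyroxine, are G3a 0 and 3, G3b 2 and 4, G4 5 and 7, G5 7 and 4. They sum to 14 and 18.
- **Same table, eGFR row.** Placebo 9.96 +/- 18.3, levothyroxine 13.35 +/- 28, p = 0.16. The notes under the table declare mean and standard deviation.
- **Secondary Outcome Measures, item 1.** eGFR at three months is the first secondary outcome, and "the glomerular filtration rate was calculated based on the seric creatinine expressed in mg / dl, the formula of CKD-EPI was use".
- **Statistical Test of Hypothesis and Method.** Continuous variables are compared between groups by t-test or Mann-Whitney U, depending on distribution. The section also allows a median to be shown with an SD.
- **Method of Estimation.** The estimate is the difference between arms in mean final values. No baseline adjustment is mentioned.

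**The concern.** A patient's CKD stage fixes the range in which that patient's eGFR lies. Fourteen of the 18 levothyroxine patients are in G3a, G3b or G4 and so have an eGFR of at least 15, and seven of these have at least 30. A mean of 13.35 looks too low for such a group. In both arms the printed SD is also about twice the printed mean, which is odd for a quantity that cannot be negative.

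The Detailed Description makes improvement in glomerular filtration rate an objective. A reader who uses this row sees arms about 3.4 ml/min/1.73m2 apart (13.35 - 9.96 = 3.39) with p = 0.16, and may conclude that renal function was balanced. A reader who sets a 3-month mean against this baseline would misjudge the change.

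**Working it through.** **Inputs.** Stage counts, stage ranges, arm sizes and the eGFR row, all from Table 1. G5 is taken to start at 0.

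**1. Are the stage counts sound?** Fisher's exact test on the counts gives p = 0.238 (G3a), 0.672 (G3b), 1.00 (G4) and 0.142 (G5). The table prints 0.23, 0.67, 1.00 and 0.14, so these are the counts that were analysed. The G3a percentage is misprinted: 3/18 = 16.7%, not 6.6%. A G3a count of 1 would give a Fisher p of 1.00, not 0.23.

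**2. Levothyroxine mean.** With every patient at the floor of the stage:

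(3x45 + 4x30 + 7x15 + 4x0)/18 = 360/18 = 20.0

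With every patient just below the next stage up:

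(3x60 + 4x45 + 7x30 + 4x15)/18 = 630/18 = 35.0

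The printed 13.35 is below the minimum.

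**3. Levothyroxine median.** The four lowest values are G5 and the next seven are G4, so the 9th and 10th ordered values are both G4. The median is at least 15, and 13.35 is not a possible median.

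**4. Levothyroxine SD.** The spread is largest with G3a and G3b at their upper limits and G4 and G5 at their floors. The mean is then (180 + 180 + 105 + 0)/18 = 25.83. The sum of squared deviations is about 8462.5, and sqrt(8462.5/17) = 22.3. The printed 28 exceeds this.

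**5. Could rounding or the G3a misprint rescue the cell?**
- If eGFR was rounded before staging, the floor is (3x44.5 + 4x29.5 + 7x14.5)/18 = 353/18 = 19.6, and the median is at least 14.5.
- If G3a were really 1 and the other two patients were in G5, the floor is (45 + 120 + 105)/18 = 15.0.

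Both floors are still above 13.35.

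**6. Placebo.** The possible mean runs from (2x30 + 5x15)/14 = 135/14 = 9.64 to (2x45 + 5x30 + 7x15)/14 = 345/14 = 24.6. The printed mean implies a total of 14 x 9.96 = 139.44. With the other seven patients at their floors, the seven G5 patients can average at most (139.44 - 135)/7 = 0.63 (1.13 if eGFR was rounded before staging). At that mean the SD cannot exceed about 11.8, against 18.3 printed. A placebo median of 9.96 is possible by itself (range 7.5 to 22.5), but the SD could then be at most about 18.1.

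**7. The p-value.** Pooled t-tests from summary figures, n = 14 and 18:

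| Figures used | Difference | Pooled SD | SE | t | p (Welch) |
|---|---|---|---|---|---|
| As printed | 3.39 | 24.28 | 8.65 | 0.39 | 0.70 (0.68) |
| Mean and SD exchanged | 9.70 | 12.00 | 4.28 | 2.27 | 0.031 (0.025) |

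Neither gives 0.16. A Mann-Whitney test on data with these stage counts could give any p from about 0.001 to 0.64. A search over data sets that also match the exchanged means and SDs gave p from about 0.01 to 0.22, so 0.16 is attainable.

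**8. The exchanged figures.** 28 +/- 13.35 and 18.3 +/- 9.96 both lie inside the limits set by the stage counts: levothyroxine mean 20.0 to 35.0 and SD 9.6 to 22.3; placebo mean 9.64 to 24.6 and SD 5.2 to 18.5.

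**The case against.** The strongest reply is that this is one misprinted row describing a secondary variable in a completed study, and that little follows from it. Much of that stands.

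- **The p-value.** A reader might infer that p = 0.16 is wrong. The documents do not support that, because they allow Mann-Whitney, the table does not name the test used, and that test could give 0.16. A mismatch with the t-test is not special to this row: from the printed summaries, age gives 0.21 against 0.41 printed, proteinuria 0.34 against 0.14, and diastolic pressure 0.43 against 0.60.
- **A spurious improvement.** A reader might infer that an arm with no change would appear to gain at least 6.65 ml/min/1.73m2 (20.0 - 13.35), or 50% of the printed baseline. That bound assumes correct stage counts and unrounded limits; with rounding it is 19.61 - 13.35 = 6.26, or 47%. It also assumes that someone compares a correct final mean with this row. The planned estimate compares final values between arms, and the documents report no change calculated from the row.
- **Imbalance already visible.** Creatinine is 3.65 against 2.46 mg/dl (p = 0.05), and G5 is 50% against 22%. A careful reader can see a renal difference without the eGFR row.

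None of this rescues the levothyroxine cell. The visible imbalance in creatinine and G5 is a further reason to correct a row that suggests the arms are close.

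**Conclusion.** The levothyroxine eGFR of 13.35 +/- 28 is impossible given the table's own stage counts. The mean must be 20.0 to 35.0 (floor about 19.6 if eGFR was rounded before staging), the median at least 15 (14.5 with rounding) and the SD at most 22.3. The placebo figure is not credible. This rests on the counts being right and coming from the same eGFR values; the arm totals and Fisher p-values support the counts. The printed p = 0.16 is unverified, not disproved.

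An exchange of mean and SD in both arms is the likeliest cause, but that is an inference. If it is the cause, the arms differ at baseline by 28 - 18.3 = 9.7 ml/min/1.73m2, in line with the creatinine and G5 rows. An unadjusted comparison of final eGFR would then carry that difference in favour of levothyroxine.

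The misprint affects the description of baseline balance and any change from baseline in eGFR. It does not enter the final-value comparison itself, and the primary outcome, 24-hour proteinuria, is untouched.

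**What to change.** 1. Recompute the eGFR mean, SD and p-value for both arms from patient-level data, name the test, and replace the row.
2. Confirm that the stage counts come from the same eGFR values, and correct the G3a percentage to 16.7%.
3. Until then, do not use the printed row to judge balance or change.
4. Compare 3-month eGFR between arms with patient-level baseline eGFR as a covariate. Do this whether or not the corrected arms differ, so that the choice of covariate does not depend on the imbalance observed. Label the analysis post hoc, because the study is complete.

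The cost is one corrected table row, from data that should already be held, and one covariate in one secondary analysis.

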**Number of Baseline Participants**

38 patients ( 19 arm Levothyroxine and 19 arm placebo)

**Number of Units Analyzed** 32 patients ( 18 arm Levothyroxine and 14 arm placebo)

**Analysis Population Type** Participants

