### Primary Outcome Measure:

1. 24 hours urine Proteinuria in patients with subclinical hypothyroidism and CKD G2-G5 without renal support therapy Randomized clinical trial of levothyroxine group versus placebo [Time Frame: three months]

Outcome Measure Description. Definition: Proteinuria was defined as the presence of proteins in the urine for 24 hours with a range greater than or equal to 0.150 grams / 24 hours. A measurement was made at the beginning and at 3 months of the study to all patients

Measure Type: mean

Measure of Dispersion/Precision: Standard Deviation

Number of Participants Analyzed: 32patients

Number of Units Analyzed: (18 arm Levothyroxine and 14 arm placebo)

Unit of Measure: grams/ 24 hours

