### **Statistical Test of Hypothesis and Method**

In the case of quantitative variables, the data are shown as average or median with standard deviation, according to the distribution, be it parametric or non-parametric, respectively.

The nominal variables are shown with frequencies or percentages.

For intergroup and continuous variable comparisons, in the case of qualitative variables, chi2 and, in the case of quantitative variables, the Student's T test or Mann-Whitney U test depending on the distribution of the sample.

The statistical analysis will be carried out with the statistical program SPSS, version 20.

In all cases a value of  $p < 0.05$  will be accepted as significant.

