### **Method of Estimation (or Statistical Test of Hypothesis or Other Statistical Analysis required)**

- Mean Difference (Final Values)
  - Risk Ratio (RR) (Adverse effects)

**Parameter Dispersion Type :** Standard Deviation

Adverse Event Information

All-Cause Mortality: no death

Eventos adversos graves: no serious adverse event

Other (Not Including Serious) Adverse Events:

During the study the following adverse effects were presented: Urinary tract infection in a single patient of the placebo group (7.14%) and nervousness in two patients of the levothyroxine group (11.11%) (RR 1.55 95% CI (0.15-15.47), value p = 1.0).

None left the study because of the adverse effect. Adverse events were not severe according to the severity scale

Table of non-serious adverse events		
arm Levothyroxine	(N=1) 7.14%	Infections and Infestations (Urinary tract infection)
Arm placebo	(N=2) 11.11%	Psychiatric Disorder (Anxiety)

Duration of urinary tract infection: five days, without complications.

Anxiety duration time: three days, without complications.

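### Enrolment is given as 32 and as 38 (19 per arm); the analysis of 32 (18 v 14) is probably complete-case with no stated sensitivity analysis, and the adverse-event table reverses its arms

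*Combined protocol and SAP*

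**What the plan says.** **Counts.** Section 6 (Detailed Description) states "Actual Enrollment: 32 participants". Number of Baseline Participants gives "38 patients ( 19 arm Levothyroxine and 19 arm placebo", and then the number analysed, "32 patients ( 18 arm Levothyroxine and 14 arm placebo". Allocation is described as 1:1.

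**Where the 32 is used.** Table 1 is headed "Placebo (n= 14 patients" for one column and 18 for the other. The Primary Outcome Measure states "Number of Participants Analyzed: 32patients", and the secondary outcomes carry the same 18 and 14. The primary outcome description also says that 24-hour protein was measured at the start and at three months in every patient.

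**Loss.** Overall Limitations and Caveats acknowledges missed follow-up in both arms, more on placebo, without counts or reasons. The adverse-event narrative says that no patient left because of an adverse effect.

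**Analysis.** Continuous outcomes are compared between groups by Student's t test or "Mann-Whitney U test depending on the distribution of the sample", and the effect measure is "Mean Difference (Final Values". The statistical sections define no analysis population and give no missing-data rule, baseline adjustment or sensitivity analysis.

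**Adverse events.** The narrative reports "Urinary tract infection in a single patient of the placebo group (7.14%) and nervousness in two patients of the levothyroxine group (11.11" per cent), with a risk ratio of 1.55 (0.15 to 15.47), p = 1.0. The table beneath it puts the single urinary infection (7.14%) in the levothyroxine row and the two anxiety events (11.11%) in the placebo row.

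**The concern.** Enrolment cannot be both 32 and 38. The 38 are already listed by arm in equal numbers, as 1:1 allocation would produce, so they look like the randomised set, with 32 being those who remained. On that reading six patients are absent from every result, five of them from placebo.

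A comparison of the retained patients can be biased if those lost differ from those kept. A reader cannot judge this, because Table 1 leaves the six out and therefore cannot show the balance achieved at randomisation. The listed analysis does not use baseline proteinuria either. Table 1 shows a gap of 1.71 - 1.28 = 0.43 g/24 h between the arms, an unknown part of which an unadjusted comparison of final values carries forward.

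The adverse-event reversal is a separate reporting error. A reader who takes only the table attributes the anxiety events to the wrong arm.

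**Working it through.** **1. Which denominators the results rest on.** The plan's only between-arm estimate is the adverse-event risk ratio, so I reproduce it first.
- On 18 and 14: (2/18)/(1/14) = 1.56. The standard error of log RR is √(1/2 - 1/18 + 1/1 - 1/14) = 1.172, giving a 95% interval of 0.16 to 15.46; Fisher p = 1.0. This matches the printed 1.55 (0.15 to 15.47) apart from rounding.
- Table 1 agrees: 11/14 = 78.57% and 13/18 = 72.22% for diabetes, as printed. The CKD stage counts sum to 14 (0 + 2 + 5 + 7) and 18 (3 + 4 + 7 + 4).

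The results therefore use the 32.

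**2. Loss by arm, if the 38 are the randomised set.**
- Levothyroxine: 19 - 18 = 1, and 1/19 = 5.3%.
- Placebo: 19 - 14 = 5, and 5/19 = 26.3%.
- Overall: 6/38 = 15.8%.
- Fisher exact test on 1/19 v 5/19: p = 0.18.

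The larger loss on placebo agrees with the limitations section. The statement that every patient was measured at three months then fits only if it refers to the 32.

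**3. How far the primary contrast could move.** No three-month result is given, so only the shift can be shown. Let dL and dP be the mean three-month proteinuria of lost minus retained patients in each arm. An arm's all-randomised mean equals its retained mean plus (fraction lost) × d. The difference (levothyroxine - placebo) therefore changes by (1/19)dL - (5/19)dP. I assume |d| between 0.5 and 1.28 g/24 h; the upper value is the printed placebo baseline SD.

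| Pattern of loss | Multiplier | at 0.5 g | at 1.28 g |
|---|---|---|---|
| Both arms, same direction | 4/19 | 0.11 g | 0.27 g |
| Placebo losses only | 5/19 | 0.13 g | 0.34 g |
| Opposite directions | 6/19 | 0.16 g | 0.40 g |

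**4. Scale.** The three-month SDs are not given, so I use the baseline SDs, 1.28 (n = 14) and 1.20 (n = 18).
- Pooled SD = √[(13 × 1.28² + 17 × 1.20²)/30] = 1.235 g.
- Standard error = 1.235 × √(1/14 + 1/18) = 0.44 g.

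The illustrated shifts run from 0.105/0.440 = 0.24 to 0.404/0.440 = 0.92 of one standard error.

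**5. Adverse-event arms.** 7.14% is 1/14 and 11.11% is 2/18. Both percentages, and the risk ratio in step 1, need one event on placebo and two on levothyroxine. That is the narrative and not the table.

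**6. Adverse events on all 38.** Assume that all 38 took study drug and that the six had no events: (2/19)/(1/19) = 2.0 (95% interval 0.20 to 20.2).

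**The case against.** The loss is disclosed: baseline and analysed counts are printed one after the other, and the imbalance is listed as a limitation. No section calls the 38 randomised or the 32 completers. The participant-flow heading carries no counts in the text available, and a figure is not shown, so numbers and reasons may be given there. This stands, and it is why the complete-case reading is an inference here. A flow figure could explain the six patients, but it could not make 32 equal 38 or supply the missing sensitivity analysis.

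The shifts are hypothetical and all lie below one standard error. They are shifts in means and do not carry over to a Mann-Whitney test. This also stands; they show scale only.

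A reader might go further in three ways that the documents do not support:

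- *That the unequal loss shows the treatment comparison is biased, or biased in a known direction.* No outcome or baseline value is given for the six. The bias is zero if lost and retained patients are alike, and also if dL = 5dP. Equally, p = 0.18 concerns only whether the loss rates differ and does not show that the loss is harmless.
- *That patients left because of tolerability.* The narrative says that none left for an adverse effect. Other selective loss remains possible.
- *That the direction of the adverse-event ratio is open, or that there is a safety signal.* The percentages and the ratio all agree with the narrative, so the table labels are a slip. With three events the intervals are too wide to indicate harm or its absence.

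**Conclusion.** The enrolment figure conflicts with the baseline count, and the adverse-event table has its arms reversed; both need correcting as printed. The analysis of 18 v 14 is in effect complete-case if the 38 were randomised, which the equal split and the acknowledged missed follow-up make likely but which no section states. On that condition 15.8% of patients are missing from every result, unevenly by arm, and the supplied text gives no way to see whether the primary result survives this. The illustrated movement of 0.11 to 0.40 g/24 h rests on assumed differences between lost and retained patients, and the 0.44 g standard error on baseline SDs standing in for three-month SDs. The true size and direction are unknown. The possible effect is moderate for so small a trial. It should be addressed, but it does not by itself overturn any result.

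**What to change.** 1. Correct the enrolment figure by reconciling 32 with 38 and with the statement that every patient was measured at three months. State the numbers randomised, treated and analysed, with losses and any known reasons by arm.
2. Label the 32-patient comparison complete-case. Also report the three-month difference adjusted for baseline proteinuria, marked post hoc because section 2 records the trial as completed.
3. Where baseline values for the six exist, show them by assigned arm beside the 32. Add a simple all-randomised sensitivity analysis: a delta shift or bounds, varied separately by arm.
4. Correct the arm labels in the adverse-event table and report events on all who took study drug.

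The cost is a little more analysis and a less certain stated result; no new data are needed. Item 3 depends on the sponsor's records. Section 6 describes baseline measurement of the variables and the primary outcome description refers to every patient, so baseline values for the six probably exist, but none are shown. With only 14 placebo outcomes, any model must stay small.
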